# 9.2.2.7 Day 8 of Courses 2 to 12\*1

- Efficacy endpoint survey
  - FACT/GOG-NTX-12
  - NRS (pain)
  - \*1 No office visit required. The survey may be performed when the subject is at home or elsewhere.

# 9.2.2.8 Day 15 (permitted window, +7 days)\*1 and Day 29 (permitted window, +7 days)\*1 of Courses 2 to 11

- Concomitant medications/therapies survey
- Investigational product administration status survey
- Postoperative adjuvant chemotherapy administration status survey
- · Adverse events survey
- Efficacy endpoints survey

- NCI-CTCAE
  - i) The worst condition noted between the preceding evaluation (excluding any unscheduled evaluation) and the day of evaluation
  - ii) Condition at the time of evaluation
- DEB-NTC
- FACT/GOG-NTX-12
- NRS (pain)
- \*1 To be performed only in the event of postponement of the administration of all drugs for postoperative adjuvant chemotherapy

# 9.2.2.9 Day 15 of Course 12 (permitted window, +7 days)

- · Concomitant medications/therapies survey
- · Adverse events survey
- Efficacy endpoints survey
  - NCI-CTCAE: The worst condition noted between the preceding evaluation (excluding any unscheduled evaluation) and the day of evaluation
  - DEB-NTC
  - FACT/GOG-NTX-12
  - FACT-G
  - NRS (pain)
- Vital sign measurement
- Laboratory tests (blood/urine)

# 9.2.3 At Discontinuation in the Treatment Period\*1

- Concomitant medications/therapies survey
- · Adverse events survey
- Efficacy endpoints survey
  - NCI-CTCAE: The worst condition noted between the preceding evaluation (excluding any unscheduled evaluation) and the day of evaluation
  - DEB-NTC
  - FACT/GOG-NTX-12
  - FACT-G
  - NRS (pain)
- · Vital sign measurement
- Laboratory tests (blood/urine)
  - \*1 If the evaluation at treatment period discontinuation takes place on or after Day 43 of the last course of postoperative adjuvant chemotherapy, or if the tests/observations for the subsequent clinical study are not possible, perform the end-of-study evaluations instead of the treatment-period discontinuation evaluations.

# 9.2.4 Follow-up Period\*1

\*1 If the subject is discontinued from the study in the follow-up period, perform the end-of-study evaluations.

# 9.2.4.1 At Study Completion (Day 43 of the last course [permitted window, +14 days])

- Concomitant medications/therapies survey
- · Adverse events survey
- Efficacy endpoints survey
  - NCI-CTCAE: The worst condition noted between the preceding evaluation (excluding any unscheduled evaluation) and the day of evaluation
  - DEB-NTC
  - FACT/GOG-NTX-12
  - FACT-G
  - NRS (pain)
- Pregnancy test (only subjects for whom the test is required)
- Vital sign measurement
- Laboratory tests (blood/urine)
- · Blood sampling for immunogenicity

# 9.2.5 At Unscheduled CIPN Evaluations (if a restricted concomitant medication is prescribed by the investigator or subinvestigator for the prevention or treatment of CIPN at any time other than the above-mentioned evaluations)\*1

- Efficacy endpoint survey
  - NCI-CTCAE: The worst condition noted between the preceding evaluation and the day of evaluation
  - \*1 An office visit is required.

#### 9.3 Subject Demographic Information Survey

The investigator or subinvestigator will determine the following information and enter it in the eCRF.

- > Initially assigned drug number
- > Day of registration
- ➤ Body height and weight (date of measurement and values), smoking status, drinking status and alcohol consumption
- > ECOG performance status
- ➤ Details of colon cancer (site [cecum/ascending colon/transverse colon/descending colon/sigmoid colon/rectosigmoid], disease stage [I/II/IIIa/IIIb/IV], date of resection)
- ➤ Comorbidities: disease(s) present at informed consent
- ➤ History: history of peripheral neuropathy (disease name, time of disease), history of CNS neuropathy (disease name, time of disease), history of diabetes mellitus (disease name, time of disease), history of alcohol abuse (time of disease)
- ➤ Details of menopause\*1 (premenopausal or <2 years since menopause/≥2 years since menopause)
  \*1 Female subjects only

# 9.4 Survey of Investigational Product Administration Status and Postoperative Adjuvant Chemotherapy Administration Status

The investigator or subinvestigator will determine the following information about the investigational product and postoperative adjuvant chemotherapy from after subject registration to study completion (Day 43 of the last course).

# [1] Investigational product

• Whether administered, the drug number of the drug actually administered, time and date of the first dose, time and date of the last dose, status of administration (entire amount/other)

# [2] Postoperative adjuvant chemotherapy

• Oxaliplatin:

Whether administered (if not administered, the reason [CIPN/adverse event/other]); any reduction from the planned dose of 85 mg/m^2 (if dose reduction took place, the reason [CIPN/adverse event/other]); time and date of the first dose; time and date of the last dose; the actual dose

#### • Levofolinate:

Whether administered (if not administered, the reason [change in fluorouracil dose/adverse event/other]); any reduction from the planned dose of 200 mg/m^2 (if dose reduction took place, the reason [change in fluorouracil dose/adverse event/other]); first day of administration

- Fluorouracil intravenous bolus:
  - Whether administered (if not administered, the reason [CIPN/adverse event/other]); any reduction from the planned dose of 400 mg/m^2 (if dose reduction took place, the reason [CIPN/adverse event/other]); first day of administration
- Fluorouracil continuous intravenous infusion:
  Whether administered (if not administered, the reason [CIPN/adverse event/other]); any reduction from the planned dose of 2,400 mg/m² (if dose reduction took place, the reason [CIPN/adverse event/other]); first day of administration; last day of administration (if the treatment ended before Day 3, the reason [CIPN/adverse event/other])

# 9.5 Survey of Concomitant Medications/Therapies

# 9.5.1 Concomitant Medications

The investigator or subinvestigator will determine the following information about the concomitant medications used from after informed consent to study completion (the day of the Day 43 evaluations in the last course).

#### 9.5.1.1 Concomitant Medications that are Neither Prohibited nor Restricted

• Name of drug, first day of administration, last day of administration

#### 9.5.1.2 Prohibited and Restricted Concomitant Medications

The information listed below will be determined for any prescription drug used that corresponds to the definition of a prohibited or restricted medication, even if the route of administration and the reason for its use are in compliance. Over-the-counter medications and ready-made transfusion preparations are considered concomitant medications described in "9.5.1.1 Concomitant medications that are neither prohibited nor restricted."

• Name of drug, route of administration, first day of administration, last day of administration, dose, reason for administration (CIPN/adverse event/other)

# 9.5.2 Concomitant Therapies

The investigator or subinvestigator will determine the following information about all therapies performed concomitantly from after informed consent to study completion.

• Name of therapy, first day of treatment, last day of treatment

# 9.6 Investigations/Observations Pertaining to Efficacy and Evaluation Methods

# 9.6.1 Efficacy Endpoints

- > Endpoints to be evaluated by the investigator or subinvestigator
  - NCI-CTCAE peripheral motor neuropathy, peripheral sensory neuropathy (CIPN only)
  - DEB-NTC
- > Endpoints to be evaluated by the subject
  - FACT/GOG-NTX-12
  - FACT-G
  - NRS (pain)
- > Other
  - Discontinuation, suspension, and dose reduction of oxaliplatin due to CIPN

The efficacy endpoints will not be classified as primary or secondary because this is an exploratory study of ART-123 for preventing the onset of oxaliplatin-induced peripheral neuropathy.

# 9.6.2 Considerations for Efficacy Evaluations

Evaluations performed on a day when the investigational product is administered will be performed before administration.

# 9.6.3 Evaluation Methods

# 9.6.3.1 NCI-CTCAE Peripheral Motor Neuropathy, Peripheral Sensory Neuropathy (CIPN only)

The investigator or subinvestigator will evaluate neuropathy as follows:

- > Assessment time points
  - Days 1, 2, 3, 15\*1, and 29\*1 of courses 1 to 11
  - Days 1, 2, 3, and 15 of course 12
  - At Study completion
  - · At Discontinuation in the Treatment Period
  - At unscheduled CIPN evaluations
    - \*1 To be performed only in the event of postponement of the administration of all drugs for postoperative adjuvant chemotherapy

- > Information to be determined and evaluated
  - Date and time point of evaluation (before investigational product administration/after investigational product administration/not applicable)
  - Evaluate the grade on a 6-step scale (none, Grade 1 to 5) for each of the evaluation classifications (peripheral motor neuropathy, peripheral sensory neuropathy) based on the NCI-CTCAE grade classification system provided in Appendix 3
  - Assess the condition at the time of evaluation on Day 1 of course 1
  - On Days 15 and 29 of courses 1 to 11 and Day 1 of courses 2 to 12, assess the worst condition noted between the preceding evaluation (excluding any unscheduled evaluation) and the day of evaluation and the condition at the time of evaluation
  - On days of evaluation other than Day 1 and Days 15 and 29 of courses 1 through 11, assess the worst condition noted between the preceding evaluation (excluding any unscheduled evaluation) and the day of evaluation. At unscheduled CIPN evaluations, assess the worst condition noted between the preceding evaluation and the day of evaluation

#### 9.6.3.2 DEB-NTC

The investigator or subinvestigator will evaluate neuropathy as follows:

- > Assessment time points
  - Days 1, 15\*1, and 29\*1 of courses 1 to 11
  - Days 1 and 15 of course 12
  - · At Study completion
  - At Discontinuation in the Treatment Period
- > Information to be determined and evaluated
  - Date and time point of evaluation (before investigational product administration/after investigational product administration/not applicable)
  - Evaluate each of the following symptoms based on the DEB-NTC grade classification system provided in Appendix 4
    - Peripheral sensory abnormalities or discomfort when touching things (Grade 0 to 2) (If Grade 1 or greater, the site of symptom: hand/foot/lip, tongue and surroundings, face/pharyngolarynx/other)
    - Painless peripheral sensory abnormalities or discomfort under normal conditions (Grade 0 to 2) (If Grade 1 or greater, the site of symptom: hand/foot/lip, tongue and surroundings, face/pharyngolarynx/other)
    - Painful peripheral sensory abnormalities or discomfort under normal conditions (Grade 0 to 2) (If Grade 1 or greater, the site of symptom: hand/foot/lip, tongue and surroundings, face/pharyngolarynx/other)
    - Functional disorders (Grade 0, 3)
    - \*1 To be performed only in the event of postponement of the administration of all drugs for postoperative adjuvant chemotherapy

#### 9.6.3.3 FACT/GOG-NTX-12

A clinical research coordinator will have subjects complete the Japanese version of the FACT/GOG-NTX-12 (Version 4, Appendix 5) questionnaire. The clinical research coordinator will collect questionnaires from subjects and enter the date and results of evaluation in the eCRF.

- > Assessment time points
  - Days 1, 8, 15\*1, and 29\*1 of courses 1 to 11
  - Days 1, 8, and 15 of course 12
  - At Study completion
  - At Discontinuation in the Treatment Period
- > Information to be determined
  - Date and time point of evaluation (before investigational product administration/after investigational product administration/not applicable)
- > Considerations for evaluations
  - If the day of an evaluation falls on the day of an office visit, inform the subject to complete the questionnaire before the efficacy evaluation by the investigator or subinvestigator.
  - To allow the evaluation of physician-evaluated severity of peripheral neuropathy independently
    from subject evaluations, the investigator or subinvestigator and clinical research coordinator
    present during the physician evaluation of peripheral neuropathy will not review evaluations
    entered by the subjects.
  - A clinical research coordinator not present during the physician evaluation of peripheral neuropathy will collect the questionnaires from the subjects and enter them in the eCRFs without informing the investigator or subinvestigator and clinical research coordinator present during the physician evaluation of peripheral neuropathy.
    - \*1 To be performed only in the event of postponement of the administration of all drugs for postoperative adjuvant chemotherapy

#### 9.6.3.4 FACT-G

The investigator or subinvestigator will have subjects complete the Japanese version of the FACT-G (Version 4, Appendix 6) questionnaire. The clinical research coordinator will collect questionnaires from subjects and enter the date and results of evaluation in the eCRF.

- > Assessment time points
  - Day 1 of courses 1, 5, and 9
  - Day 15 of course 12
  - At Study completion
  - At Discontinuation in the Treatment Period
- > Information to be determined
  - Date and time point of evaluation (before investigational product administration/after investigational product administration/not applicable)

# 9.6.3.5 NRS (pain)

[figure not shown]
The investigator or subinvestigator will have subjects evaluate the severity of pain at the site subject to evaluation based on the NRS. The clinical research coordinator will collect the evaluation forms from subjects and enter the date and results of evaluation in the eCRF.

- > Assessment time points
  - Days 1, 8, 15\*1, and 29\*1 of courses 1 to 11
  - Days 1, 8, and 15 of course 12
  - · At Study completion
  - At Discontinuation in the Treatment Period

•

- > Sites subject to evaluation
  - Hands
  - Feet
- ➤ Date and time point of evaluation (before investigational product administration/after investigational product administration/not applicable)
  - \*1 To be performed only in the event of postponement of the administration of all drugs for postoperative adjuvant chemotherapy

# Numerical Rating Scale (NRS)

0: no pain at all; 10: the most severe pain imaginable

#### 9.7 Investigations/Observations Pertaining to Safety and Evaluation Methods

# 9.7.1 Vital Signs

The investigator or subinvestigator will measure body temperature, blood pressure, and pulse rate. Vital signs will be measured with the subjects at rest.

- ➤ Measurement time points
  - · Screening period
  - Day 1 of courses 2 to 12
  - Day 15 of course 12
  - · At Study completion
  - · At Discontinuation in the Treatment Period

•

- Parameters
  - Axillary temperature
  - Sitting systolic/diastolic blood pressure
  - Sitting pulse rate
- > Information to be determined

- Date and time point of measurement (before investigational product administration/after investigational product administration/not applicable)
- · Results

# 9.7.2 Laboratory Tests

The investigator or subinvestigator will collect samples from subjects at the following measurement time points and have the samples analyzed at the study site.

- > Measurement time points
  - Screening period\*1
  - Day 1 of courses 2 to 12\*2
  - Day 15 of course 12
  - At Study completion
  - At Discontinuation in the Treatment Period

# > Laboratory test parameters

- Routine blood tests: Red blood cell count, haemoglobin, haematocrit, white blood cell count, white blood cell differential (neut, lympho, mono, eosino, baso), platelet count
- Clinical chemistry tests: AST (GOT), ALT (GPT), ALP, LDH, total bilirubin, total protein, albumin, BUN, creatinine, glucose, uric acid, electrolytes (Na, K, Cl)
- Urine analysis: Protein (qualitative), glucose (qualitative), occult blood (qualitative)
- Immunological assays\*3: HBs antigen, HBc antibody, HBs antibody, HBV-DNA\*4
- Coagulation tests: PT-INR, activated partial thromboplastin time, fibrinogen

#### > Information to be determined

- Dates of blood/urine sampling, time points of blood/urine sampling (before investigational product administration/after investigational product administration/not applicable)
- Results (routine blood tests, clinical chemistry tests, urine analysis, coagulations tests)
  - \*1 To be performed between Day -7 and Day -1 (one day before registration)
  - \*2 May be determined on the day before Day 1
  - \*3 To be performed only in the screening period to determine eligibility. Test data obtained within 6 months before registration may be used.
  - \*4 In cases where the test result is positive for HBc antibody or HBs antibody

# 9.7.3 Immunogenicity (anti-drug antibodies, neutralising antibodies)

The investigator or subinvestigator will collect samples from the subjects at the time points listed below, separate the serum, and temporarily store the serum before submitting the samples to the immunogenicity assay laboratory. Samples will be collected, processed, stored, and shipped as directed in written procedures to be submitted by the sponsor to each study site. The immunogenicity assay laboratory will conduct assays of anti-drug antibodies and neutralising antibodies and submit the results to the sponsor after unblinding. As the sponsor will be electronically notified of the results, the data need not be input into the eCRFs. Only the dates and time points of blood sampling should be entered.

#### > Measurement time points

- Before investigational product administration on Day 1 of course 1
- At study completion
- ➤ Blood sample volume: 6 mL
- > Information to be determined
  - Date and time point of blood sampling (before investigational product administration/after investigational product administration/not applicable)

#### 9.7.4 Adverse Events

#### 9.7.4.1 Definition of Adverse Events

An adverse event is defined as any untoward or unintended disease or sign (including abnormal laboratory findings and vital signs) that occurs after informed consent. Any adverse event occurring after investigational product administration is considered a treatment-emergent adverse event (TEAE). When a diagnosis can appropriately be assigned for an adverse event, that diagnosis rather than the symptom or sign will be the adverse event name. Abnormal laboratory findings and vital signs are constituted when:

- [1] An abnormal laboratory finding or vital sign satisfies the definition of a serious adverse event.
- [2] An abnormal laboratory finding or vital sign results in the suspension or discontinuation of the investigational product.
- [3] An abnormal laboratory finding or vital sign results in the use of a drug or intervention for treatment.
- [4] The physician determines that an abnormal laboratory finding or vital sign is of a medically significant severity (e.g., is an abnormality consistent with [2] or [3] above but there was no opportunity for intervention).

CIPN will not be considered an adverse event in this study.

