## 3.2 Exclusion Criteria

The presence of any of the following at the time of registration will exclude the patient from this study:

- [1] History of hypersensitivity to any of the ingredients in thrombomodulin alfa (recombinant)
- [2] Peripheral neuropathy or central nervous system (CNS) damage
- [3] Mental disorder of a severity that would affect the efficacy and safety evaluations in this study
- [4] Any treatment history of systemic chemotherapy (including any drug in the clinical trial stage) or radiotherapy intended to provide an anti-tumor effect
- [5] Active double cancer\*1
  - \*1 Synchronous double cancer or metachronous double cancer with disease-free period of no more than 5 years; does not include lesions equivalent to carcinoma in situ or intramucosal carcinoma deemed to have resolved with local treatment
- [6] Yet to recover from an operation or a complication such as a postoperative infection
- [7] Serious intestinal obstruction, diarrhoea, or pyrexia

- [8] History of cerebrovascular disorder (e.g., cerebral haemorrhage, cerebral infarction) within 52 weeks (364 days) before informed consent
- [9] Intracranial haemorrhage, pulmonary haemorrhage, or gastrointestinal haemorrhage (persistent haematemesis/blood in stool or gastrointestinal ulcer-induced haemorrhage)
- [10] Unconfirmed completion of a haemostasis procedure after CNS surgery or after trauma
- [11] Receiving transfusion, a blood derivative, G-CSF, or another hematopoietic factor within 7 days before the laboratory tests performed to assess registration eligibility
- [12] Hepatitis B infection and a positive test result for HBs antigen. Patients negative for HBs antigen but positive for HBc or HBs antibody must undergo an HBV-DNA test. A result at or above the normal range will disqualify the patient from enrollment. Test data obtained within 6 months before registration may be used.
- [13] A positive test result for HIV antigen or antibody
- [14] Establishment of an artificial anus (even if temporary) in colorectal cancer surgery
- [15] Administration of another investigational product within 16 weeks (112 days) before informed consent or undergoing observation that is still ongoing a day before informed consent
- [16] Pregnancy or possible pregnancy; wish to become pregnant during the study period; breastfeeding
- [17] Having participated in this study in the past
- [18] Prior treatment history with thrombomodulin alfa (recombinant)

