# 10.2 Particularly Notable Information

# 10.2.1 Precautions Related to Bleeding

Because Recomodulin has anticoagulant activity and could potentially cause or exacerbate bleeding symptoms, the drug must be administered with bleeding symptoms sufficiently managed. If a bleeding-related serious adverse event occurs, Recomodulin administration will be discontinued as necessary, and appropriate intervention, such as transfusion, will be provided as necessary.

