#### 12.7 Safety Analysis

#### 12.7.1 Analysis of Adverse Events

TEAEs evaluated in the study will conform to the definition in Section 9.7.4.1. All TEAEs identified from the first day of investigational product administration to study completion (Day 43 of the last course) will be included in the tabulations. The numbers of subjects with a TEAE in each treatment group will be tabulated by adverse event name, organ class, severity (per NCI-CTCAE grading), seriousness classification, causality, and the timing of onset. Differences from the placebo group in TEAE incidences will be calculated along with two-sided 95% confidence intervals of these differences.

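### The adverse event and TEAE definitions have no worsening clause, so an event that begins before the first dose and worsens after it has no stated route into the placebo comparison

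*Protocol*

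**What the plan says.** Section 9.7.4.1 fixes two definitions. The first reads: "An adverse event is defined as any untoward or unintended disease or sign (including abnormal laboratory findings and vital signs) that occurs after informed consent". The second, for treatment emergence, reads: "Any adverse event occurring after investigational product administration is considered a treatment-emergent adverse event (TEAE". Conditions already present at consent go to a separate record, listed in Section 9.3 as "Comorbidities: disease(s) present at informed consent".

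Section 9.2.1 starts the adverse event survey in screening, which runs from Day -14 to Day -1. Events can therefore be on record before any investigational product is given. For each event, Section 9.7.4.2 lists one date of occurrence and one severity among the items to be determined. It lists no date or grade of worsening.

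Section 12.7.1 makes the definition binding on the analysis: "TEAEs evaluated in the study will conform to the definition in Section 9.7.4.1". It then sets the comparison: "Differences from the placebo group in TEAE incidences will be calculated along with two-sided 95% confidence intervals of these differences".

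Section 10.2.1 describes the product's main pharmacological hazard: "Because Recomodulin has anticoagulant activity and could potentially cause or exacerbate bleeding symptoms".

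**The concern.** The risk statement in Section 10.2.1 has two parts, causing bleeding and making existing bleeding worse. The definition behind the safety tables plainly covers the first part and is silent on the second.

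Two kinds of case are affected:

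- An event that begins in the screening window and rises in grade after dosing.
- A comorbidity present at consent that worsens on treatment.

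If the product does exacerbate such conditions, the lost cases would fall more often in the ART-123 groups, and the difference from placebo would be pulled towards no harm. Blinding makes site habits similar across groups, but it does not bring back events that were never entered or were dated before the first dose.

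**Working it through.** This is mainly a question of wording, so the relevant sections are set side by side for each kind of case.

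**Case A: begins between consent and first dose, worsens after dosing.**

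1. It occurs after consent, so it is an adverse event (9.7.4.1).
2. Its one date of occurrence precedes the first dose (9.7.4.2).
3. A TEAE must occur after product administration (9.7.4.1), and 12.7.1 tabulates only events meeting that definition.
4. No rule says that a rise in grade opens a new record or changes the date. As written, the event is not a TEAE.

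**Case B: present at consent, worsens after dosing.**

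1. The condition is recorded as a comorbidity (9.3).
2. Whether its worsening is an untoward sign that occurs after consent is left to the investigator. One site may enter it and another may not.
3. If it is entered with a post-dose date, it is a TEAE. If not, it appears nowhere in 12.7.1.

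**What narrows the exposure.**

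- Exclusion [9] in Section 3.2 removes "Intracranial haemorrhage, pulmonary haemorrhage, or gastrointestinal haemorrhage (persistent haematemesis/blood in stool or gastrointestinal ulcer-induced haemorrhage"; exclusion [6] removes subjects not yet recovered from surgery or its complications. Both apply at registration, which Section 9.2.2.1 places on Day 1 of course 1 before dosing. A listed haemorrhage that starts after consent and is still present on Day 1 therefore also excludes the subject.
- Section 9.7.4.1, items [1] to [4], counts laboratory and vital sign abnormalities that are serious, lead to suspension or discontinuation of product, are treated, or are judged medically significant. None of the four requires a normal baseline.
- Laboratory parameters, including the coagulation tests, are summarised separately by time point and group (9.7.2, 12.7.2).

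What remains is mostly bleeding outside the listed types, and non-bleeding conditions that are not laboratory findings.

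**Size per subject.** The plan's design figure is 25 per group for a precision of ±20% (12.1). It reproduces: 1.96 × √(0.5 × 0.5 / 25) = 0.196. With 25 as the denominator, one subject whose only event is an uncounted worsening moves the group's incidence by 1/25 = 4 percentage points.

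**Illustration on assumed counts (not from the protocol).** Take 1 of 25 placebo subjects with a bleeding TEAE and 3 of 25 in one ART-123 group, with Wald intervals, d ± 1.96 × √(p₁(1−p₁)/25 + p₀(1−p₀)/25):

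| ART-123 cases counted | Difference from placebo | 95% interval |
|---|---|---|
| 3 (no worsened case) | 8.0 points | −6.9 to 22.9 |
| 4 (one worsened case added) | 12.0 points | −4.3 to 28.3 |
| 5 (two worsened cases added) | 16.0 points | −1.5 to 33.5 |

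The table shows sensitivity only. It does not estimate how many such cases would arise.

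**The case against.** A reader might infer that the definition admits only events that start after dosing, so that bleeding exacerbation drops out of the safety comparison altogether. The text does not go that far. It speaks of events occurring, and contains neither a restriction to new onset nor an exclusion of worsening. An investigator could properly enter a post-dose exacerbation as a new untoward sign, and it would then be a TEAE. The follow-up rule in Section 9.7.4.5, which refers to a return to baseline level, fits that reading. This objection stands for conditions present at consent. It is weaker for an event already recorded with a pre-dose date, because nothing tells the site to open a second record.

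A reader might also infer that half of the named bleeding risk is lost. The protocol gives no frequencies for causing versus exacerbating bleeding, and the entry criteria remove the main pre-existing haemorrhages. That inference has no support.

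Serious exacerbations have a reporting route. Section 10.2.1 foresees them ("If a bleeding-related serious adverse event occurs"), and Section 10.3.1 requires notification within 24 hours. That protects the subject, but it does not make an event with a pre-dose date a TEAE under 12.7.1.

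Finally, the data entry handbook mentioned in Section 15.1 or the statistical analysis plan could settle how worsening is recorded. Neither is at hand, and nothing is inferred from their absence. But the definition and its use in the analysis are fixed in the protocol itself, and an analysis plan cannot recover a date of worsening that sites were not asked to record.

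**Conclusion.** The point holds in limited form. The definitions are silent on worsening, and the silence is carried into the placebo comparison by reference. As written, an event that begins before the first dose and worsens afterwards is not a TEAE. Worsening of a comorbidity may be omitted or counted inconsistently. This does not match the exacerbation risk that the protocol itself names.

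A systematic exclusion of bleeding exacerbation, or a bias of known size, is not shown. The number of affected subjects is unknown and may be small. The 4-point shift per subject assumes 25 analysed subjects in the group and a subject with no other event in the same category. The direction, towards no harm, holds only if ART-123 does worsen such conditions more often than placebo. The change is still worth making, because the groups are small and the correction is cheap.

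**What to change.** In Section 9.7.4.1, define an adverse event as an untoward or unintended disease or sign that newly occurs or worsens after consent. Define a TEAE as an adverse event that starts, or increases in CTCAE grade or becomes serious, after the first dose of investigational product relative to the pre-dose state.

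In Section 9.7.4.2, have a post-dose worsening entered as a separate record with its own date and grade. Section 12.7.1 then follows by its existing cross-reference and needs no change.

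The cost is two sentences of definition and one eCRF entry instruction. The downside is a few more adverse event entries and slightly higher TEAE counts in all groups, placebo included.
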